8.1.1 Post Study Treatment Study Follow-up

In this study, efficacy as measured by EASI is a key endpoint of the study. Post study follow-up is of critical importance and is essential to preserving participant safety and the integrity of the study. Participants who discontinue study treatment must continue to be followed (in this study or a rollover study) for collection of outcome and/or survival follow-up data as required and in line with [Section 2](#) until death or the conclusion of the study.

If a patient withdraws before completion, every effort should be made to complete the assessments of the Follow-up Visits.

8.2 Discontinuation from the Study

Participants who request to discontinue study treatment will remain in the study and must continue to be followed for protocol specified follow-up procedures. The only exception to this is when a participant specifically withdraws consent for any further contact with him/her or persons previously authorized by participant to provide this information.

- Participants should notify the investigator of the decision to withdraw consent from future follow-up **in writing**, whenever possible.
- The withdrawal of consent should be explained in detail in the medical records by the investigator, as to whether the withdrawal is from further treatment with study treatment only or also from study procedures and/or post treatment study follow-up, and entered on the appropriate eCRF page.
- In the event that vital status (whether the participant is alive or dead) is being measured, publicly available information should be used to determine vital status only as appropriately directed in accordance with local law.
- If the participant withdraws consent for disclosure of future information, the sponsor may retain and continue to use any data collected before such a withdrawal of consent.

8.3 Lost to Follow-Up

- All reasonable efforts must be made to locate participants to determine and report their ongoing status. This includes follow-up with persons authorized by the participant.
- Lost to follow-up is defined by the inability to reach the participant after a minimum of **three** documented phone calls, faxes, or emails as well as lack of response by participant to one registered mail letter. All attempts should be documented in the participant's medical records.
- If it is determined that the participant has died, the site will use permissible local methods to obtain date and cause of death.
- If investigator's use of third-party representative to assist in the follow-up portion of the study has been included in the participant's informed consent, then the investigator may use a Sponsor retained third-party representative to assist site staff with obtaining participant's contact information or other public vital status data necessary to complete the follow-up portion of the study.
- The site staff and representative will consult publicly available sources, such as public health registries and databases, in order to obtain updated contact information.
- If after all attempts, the participant remains lost to follow-up, then the last known alive date as determined by the investigator should be reported and documented in the participant's medical records.

9 STUDY ASSESSMENTS AND PROCEDURES

- Study procedures and timing are summarized in the Schedule of Activities.
- Protocol waivers or exemptions are not allowed.
- All immediate safety concerns must be discussed with the Sponsor immediately upon occurrence or awareness to determine if the participant should continue or discontinue treatment.
- Adherence to the study design requirements, including those specified in the Schedule of Activities, is essential and required for study conduct.
- All screening evaluations must be completed and reviewed to confirm that potential participants meet all eligibility criteria before randomization. The investigator will maintain a screening log to record details of all participants screened and to confirm eligibility or record reasons for screening failure, as applicable.
- Procedures conducted as part of the participant's routine clinical management (eg, blood count) and obtained before signing of informed consent may be utilized for screening or baseline purposes provided the procedure meets the protocol-defined criteria and has been performed within the timeframe defined in the Schedule of Activities.

9.1 Efficacy Assessments

Efficacy assessments completed by the investigator include vIGA-AD, Eczema Area and Severity Index (EASI), and % Body Surface Area (BSA) worksheet. Every effort should be made to ensure that the same assessor conducts the assessments at all study visits for a given participant.

9.1.1 Validated Investigator Global Assessment for Atopic Dermatitis (vIGA-AD)

The vIGA-AD is a static 5-point assessment intended to assess the global severities of key acute clinical signs of AD, including erythema, induration/papulation, and oozing/crusting (lichenification excluded).¹¹² The rating of cleared (0), almost cleared (1), mild (2), moderate (3), and severe (4) will be assessed at each scheduled visit, and at unscheduled clinic visits, if applicable. Refer to [Appendix 8](#).

The vIGA-AD will be collected prior to the EASI.

9.1.2 Eczema Area and Severity Index (EASI)

The EASI is a validated, composite scoring system assessed by the investigator based on the extent of each of the 4 body regions (head and neck, upper limbs, lower limbs, and trunk) affected with AD and the intensity of each of 4 key signs of AD (erythema, induration/papulation, excoriation, and lichenification) and is based on a 4-point scale of 0 (absent), 1 (mild), 2 (moderate), and 3 (severe).¹¹³ For each of the 4 body regions, the mean intensity of inflamed lesions for each of the 4 signs is recorded. Xerosis, scaling, urticaria, or post-inflammatory pigmentation changes are not included. The total EASI score ranges from 0 to 72. The EASI will be collected at each scheduled and unscheduled clinic visit, if applicable. Further details of the evaluation and calculation of the EASI score are provided in [Appendix 9](#).

9.1.3 Body Surface Area (BSA)

A widely used method of measuring BSA involvement by AD, is the rule of nines in which for each section of the body (the possible highest score for each region is: head and neck [9%], anterior trunk [18%], back [18%], upper limbs [18%], lower limbs [36%], genitals [1%]) and will be reported as a percentage of all major body sections combined.^{114,115} Participants will undergo this assessment at each scheduled and unscheduled clinic visit, if applicable. Refer to [Appendix 10](#).

9.1.4 Pruritus and Sleep Quality Numerical Rating Scale (NRS)

Participants will complete a daily diary recording the intensity of their pruritus and the average quality of sleep they experienced during the preceding 24 hours. The intensity of pruritus will be assessed using a validated 11-point NRS, ranging from 0 (“no itching”) to 10 (“the worst itching imaginable”). The quality of sleep will be assessed using a validated 11-point NRS ranging from 0 (“the best possible sleep”) to 10 (“the worst possible sleep”) provided in [Appendix 11](#).^{116,117}

9.1.5 Dermatology Life Quality Index (DLQI)

The DLQI is a 10-item, easy-to-use, self-administered, assessment of the participants’ perception of the impact of their skin disease on different aspects of their Quality of Life (QOL) over the previous week. The DLQI score ranges from 0 (no effect on the participant’s life) to 30 (extremely large effect on the participant’s life). For each item, the scale is rated as follows: 0 = ‘not at all’/‘not relevant’; 1= ‘a little’; 2= ‘a lot’; 3= ‘very much’/‘yes’ in question 7, with an overall scoring system of 0 to 30; a high score is indicative of a poor QOL.¹¹⁸ The DLQI will be assessed at every scheduled and unscheduled clinic visit, if applicable. Refer to [Appendix 12](#).

9.1.6 Patient Oriented Eczema Measure (POEM)

The POEM is a validated tool used for monitoring atopic eczema severity. It is a 7-item questionnaire completed by the subject to assess the severity of eczema over the last week and evaluates itch, sleep disturbance, skin bleeding, skin weeping or oozing, skin cracking, skin flaking, and skin dryness. Each item has the following response options: 0 = No Days, 1 = 1-2 Days, 2 = 3-4 Days, 3 = 5-6 Days and 4 = Every Day. A total score is calculated by summing each item and results in a score ranging from 0-28. The subject will complete the questionnaire onsite at study visits. Refer to [Appendix 13](#).

9.1.7 Patient Global Impression of Change (PGI-C)

The PGI-C is a global rating anchor scale and has been used across different therapeutic categories to interpret the scores from participant-reported outcome measurements. The PGI-C will be used in this study to confirm the threshold for meaningful change on other patient reported outcomes instruments in the target patient population. Participants will be asked the following question as per the schedule of assessments: “Compared to the beginning of the study, before you started the study treatment, which of the following best describes the skin symptoms of your atopic dermatitis today?” The response choices will be as follows: much improved, moderately improved, a little improved, the same, a little worse, moderately worse, or much worse. Refer to [Appendix 14](#).

9.1.8 Patient Global Impression of Severity (PGI-S)

The PGI-S is a global rating anchor scale and has been used across different therapeutic categories to interpret the scores from participant-reported outcome measurements. The PGI-S will be used in this clinical trial to confirm the threshold for meaningful change on other PRO instruments in the target population. The PGI-S is not subject to recall error and can be also used to assess change from baseline data. Participants will be asked the following question as per the schedule of assessments, “Which of the following best describes the severity of the skin symptoms of your atopic dermatitis over the past 7 days?” The response choices will be as follows: none, mild, moderate, severe, or very severe. Refer to [Appendix 15](#).

9.2 Adverse Events

The definitions of an AE or serious adverse event (SAE) can be found in [Appendix 3](#).

AEs will be reported by the participant (or, when appropriate, by a caregiver or surrogate).

The investigator and any designees are responsible for detecting, documenting, and reporting events that meet the definition of an AE or SAE and remain responsible for following up AEs that are serious, considered related to the study treatment or the study, or that caused the participant to discontinue before completing the study.

Contacts for SAE reporting specified in Appendix 3

Adverse events of interest (AEIs) are described in Section 9.2.8.

9.2.1 Time Period and Frequency for Collecting AE and SAE Information

[Appendix 1](#) in the Investigator’s Brochure (IB) represent the Reference Safety Information to determine expectedness of serious adverse events for expedited reporting.

All SAEs must be collected from the time of signing the consent, including those thought to be associated with protocol-specified procedures and within 30 days of discontinuation of dosing.

The investigator must report any SAE that occurs after these time periods and that is believed to be related to study drug or protocol-specified procedure (eg, a follow-up skin biopsy).

- Medical occurrences that begin before the start of study treatment but after obtaining informed consent will be recorded on the appropriate section of the CRF module.
- All SAEs will be recorded and reported to Sponsor or designee within 24 hours, as indicated in [Appendix 3](#).
- The investigator will submit any updated SAE data to the sponsor or designee within 24 hours of updated information being available.

Investigators are not obligated to actively seek AEs or SAEs in former study participants. However, if the investigator learns of any SAE, including a death, at any time after a participant has been discharged from the study, and he/she considers the event reasonably related to the study treatment or study participation, the investigator must promptly notify the sponsor.

The method of evaluating and assessing causality of AEs and SAEs and the procedures for completing and reporting/transmitting SAE reports are provided in [Appendix 3](#).

9.2.2 Method of Detecting AEs and SAEs

Adverse events can be spontaneously reported or elicited during open-ended questioning, examination, or evaluation of a participant. Care should be taken not to introduce bias when collecting AE and/or SAEs. Inquiry about specific AEs should be guided by clinical judgement in the context of known adverse events, when appropriate for the program or protocol.

9.2.3 Follow-up of AEs and SAEs

- Nonserious AEs should be followed to resolution or stabilization, or reported as SAEs if they become serious (see [Section Appendix 3](#)).
- Follow-up is also required for nonserious AEs that cause interruption or discontinuation of study treatment and for those present at the end of study treatment as appropriate.
- All identified nonserious AEs must be recorded and described on the nonserious AE page of the CRF (paper or electronic). Completion of supplemental CRFs may be requested for AEs and/or laboratory abnormalities that are reported/identified during the course of the study.

After the initial AE/SAE report, the investigator is required to proactively follow each participant at subsequent visits/contacts. All SAEs, and non-serious AEs of interest (as defined in [Section 9](#)) will be followed until resolution, until the condition stabilizes, until the event is otherwise explained, or until the participant is lost to follow-up (as defined in [Section 8.3](#)).

Further information on follow-up procedures is given in [Appendix 3](#).

9.2.4 Regulatory Reporting Requirements for SAEs

- Prompt notification by the investigator to the Sponsor of SAEs is essential so that legal obligations and ethical responsibilities towards the safety of participants and the safety of a product under clinical investigation are met.
- An investigator who receives an investigator safety report describing SAEs or other specific safety information (eg, summary or listing of SAEs) from the Sponsor will file it along with the Investigator's Brochure and will notify the IRB/IEC, if appropriate according to local requirements.

Sponsor or designee will be reporting AEs to regulatory authorities and ethics committees according to local applicable laws including European Directive 2001/20/EC and FDA Code of Federal Regulations 21 CFR Parts 312 and 320. A SUSAR (Suspected, Unexpected Serious Adverse Reaction) is a subset of SAEs and will be reported to the appropriate regulatory authorities and investigators following local and global guidelines and requirements.

9.2.5 Pregnancy

If, following initiation of the study treatment, it is subsequently discovered that a participant is pregnant or may have been pregnant at the time of study exposure, including during at least for 3 months after study product administration, the investigator must immediately notify the BMS Medical Monitor/designee of this event and complete and forward a Pregnancy Surveillance Form to BMS Designee within 24 hours of awareness of the event and in accordance with SAE reporting procedures described in [Appendix 3](#).

If the investigator determines a possible favorable benefit/risk ratio that warrants continuation of study treatment, or re-initiation of study treatment, a discussion between the investigator and the BMS Medical Monitor/designee must occur.

Follow-up information regarding the course of the pregnancy, including perinatal and neonatal outcome and, where applicable, offspring information must be reported on the Pregnancy Surveillance Form.

Any pregnancy that occurs in a female partner of a male study participant should be reported to Sponsor or designee. In order for Sponsor or designee to collect any pregnancy surveillance information from the female partner, the female partner must sign an informed consent form for disclosure of this information. Information on this pregnancy will be collected on the Pregnancy Surveillance Form.

If any sexual activity (eg, vaginal, anal, oral) has occurred between a male participant and a pregnant partner(s) without the use of a condom during and at least for 3 months, after study product administration, the information should be reported to the Sponsor or designee, even if the male participant has undergone a successful vasectomy.

In order for Sponsor or designee to collect any pregnancy surveillance information from the female partner, the female partner(s) must sign an informed consent form for disclosure of this information. Information on the pregnancy will be collected on the Pregnancy Surveillance Form.

9.2.6 Laboratory Test Result Abnormalities

The following laboratory test result abnormalities should be captured on the nonserious AE CRF page or SAE Report Form electronic, as appropriate. Paper forms are only intended as a back-up option when the electronic system is not functioning.

- Any laboratory test result that is clinically significant or meets the definition of an SAE
- Any laboratory test result abnormality that required the participant to have study treatment discontinued or interrupted
- Any laboratory test result abnormality that required the participant to receive specific corrective therapy

It is expected that wherever possible, the clinical rather than laboratory term would be used by the reporting investigator (eg, anemia versus low hemoglobin value).

Clinically significant changes, in the judgment of the investigator, in laboratory parameters (abnormalities) will be recorded as AEs. During the treatment period, all total WBC and WBC differential results will be blinded. Reductions in ALC levels is a known PD effect of BMS-986166. If any of the following results are observed, the investigator will be notified and asked to repeat the laboratory tests within approximately 7 days:

- Absolute lymphocyte count [ALC] < 200 cells/ μ L
- Absolute neutrophil count [ANC] < 1000 cells/ μ L
- Total WBC > 20,000 cells/ μ L

If the repeat values also exceed these limits, the investigator will be informed that the patient's results for the abnormal parameter have fallen below the acceptable threshold.

If ANC or total WBC counts are confirmed below the acceptable limits, the Medical Monitor will contact the treating investigator to request close monitoring for risk of serious infection and appropriate follow-up, at the discretion of the investigator.

If the ALC is confirmed < 200 cells/ μ L, the investigator will discontinue investigational drug and then consult with the Medical Monitor. Laboratory testing will be repeated weekly until ALC is > 500 cells/ μ L.

If participants have elevations in ALT and/or AST \geq 3x the upper limit of normal (ULN), a retest should be performed as soon as possible but not later than 4 days after the original test. If the abnormality is confirmed, twice-weekly testing should occur until ALT and AST are < 3x ULN. If the ALT and/or AST stabilizes at a level > 3x ULN, the Medical Monitor may agree to less frequent testing. Other liver-related laboratory testing, including international normalized ratio (INR), alkaline phosphatase (AP), gamma-glutamyl transferase (GGT), hepatitis serologies, and other tests as deemed necessary by the investigator should be performed to better understand the observation.

The investigator should establish causality. In addition, the confirmed elevation $> 3x$ ULN is an AEI (see [Section 9.2.8](#)) and should be reported by the investigator. At any time, if any of the following occur and there are no apparent alternative causes for the finding, the investigational drug must be permanently discontinued:

- ALT or AST $> 8x$ ULN or
- ALT or AST $> 5x$ ULN with confirmation, within 2 weeks or
- ALT or AST $> 3x$ ULN and (total bilirubin $> 2x$ ULN or INR > 1.5) or
- ALT or AST $> 3x$ ULN with the appearance of fatigue, nausea, vomiting, right upper quadrant pain or tenderness, fever, rash, and/or eosinophilia ($>5\%$).

The investigator should establish causality. After discontinuation due to elevation of ALT or AST $> 5x$ ULN or concurrent elevations of ALT or AST $> 3x$ ULN and bilirubin $> 2x$ ULN, further liver function evaluation should be performed (for example, coagulation panel and alkaline phosphatase) in consultation with the Medical Monitor.

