8 DISCONTINUATION CRITERIA

8.1 Discontinuation from Study Treatment

Participants MUST discontinue investigational product (and non-investigational product at the discretion of the investigator) for any of the following reasons:

- Participant's request to stop study treatment. Participants who request to discontinue study treatment will remain in the study and must continue to be followed for protocol specified follow-up procedures. The only exception to this is when a participant specifically withdraws consent for any further contact with him/her or persons previously authorized by participant to provide this information
- Any clinical adverse event (AE), laboratory abnormality or intercurrent illness which, in the opinion of the investigator, indicates that continued participation in the study is not in the best interest of the participant
- Termination of the study by Bristol-Myers Squibb (BMS)
- Loss of ability to freely provide consent through imprisonment or involuntary incarceration for treatment of either a psychiatric or physical (eg, infectious disease) illness. (Note: Under specific circumstances and only in countries where local regulations permit, a participant who has been imprisoned may be permitted to continue as a participant. Strict conditions apply and BMS approval is required.)
- Asthma or COPD that requires systemic glucocorticoid or biologic treatment, or inhaled budesonide or equivalent at >1200 µg/day or fluticasone propionate at > 880 µg/day along with another anti-asthma/COPD drug such as a long-acting beta-agonist.
- Systemic or photo-based rescue therapy for AD ([Section 7.7.2](#)),
- Replication-competent (live) vaccine
- Grade 4 lymphopenia (ALC < 200) with repeat testing within 7 days (according to the Common Toxicity Criteria for Adverse Events [CTCAE] version 5.0)
- Elevation of ALT or AST > 5x ULN or concurrent elevations of ALT or AST > 3x ULN and bilirubin > 2x ULN
- Decline in PFT values (FEV1 and/or FVC) below 30% of the baseline values
- Diagnosis of macular edema, retinal or choroidal disease or syndrome
- Grade 2 or higher cardiac or bone marrow adverse events (with exception of ALC) according to the CTCAE version 5.0.
- Grade 3 for other system adverse events (according to the CTCAE version 5.0)
- Missed dose of ≥ 3 consecutive days or overall compliance < 85% over a period of > 30 days starting from study Day 1.

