
Any abnormal laboratory test results (hematology, clinical chemistry, or urinalysis) or results from other safety assessments (eg, electrocardiograms, radiological scans, vital signs measurements), including those that worsen from baseline, considered clinically significant in the medical and scientific judgment of the investigator. Note that abnormal lab tests or other safety assessments should only be reported as AEs if the final diagnosis is not available. Once the final diagnosis is known, the reported term should be updated to be the diagnosis.Exacerbation of a chronic or intermittent pre-existing condition including either an increase in frequency and/or intensity of the condition.New conditions detected or diagnosed after study intervention administration even though it may have been present before the start of the study.Signs, symptoms, or the clinical sequelae of a suspected drug-drug interaction.Signs, symptoms, or the clinical sequelae of a suspected overdose of either study intervention or a concomitant medication. Overdose, as a verbatim term (as reported by the investigator), should not be reported as an AE/serious adverse event (SAE) unless it is an intentional overdose taken with possible suicidal/self-harming intent. Such overdoses should be reported regardless of sequelae and should specify "intentional overdose" as the verbatim term.
Events NOT Meeting the AE Definition

Medical or surgical procedure (eg, endoscopy, appendectomy): the condition that leads to the procedure is the AE.Situations in which an untoward medical occurrence did not occur (social and/or convenience admission to a hospital).

DEFINITION OF SAE

If an event is not an AE per definition above, then it cannot be an SAE even if serious conditions are met.

SERIOUS ADVERSE EVENTS

A Serious Adverse Event (SAE) is defined as any untoward medical occurrence that, at any dose:
Results in death.
Is life-threatening (defined as an event in which the participant was at risk of death at the time of the event; it does not refer to an event which hypothetically might have caused death if it were more severe).

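### With white-cell results blinded, no one is assigned to apply the eosinophilia part of the liver stop, and the low total-WBC step has no low limit to start it

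*Combined protocol and SAP*

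**What the plan says.** Section 9.2.6 sets the blind: "During the treatment period, all total WBC and WBC differential results will be blinded". Section 9.4.9 adds that WBC and lymphocyte counts are monitored centrally and withheld from the site to avoid unblinding the investigator. The differential, which includes eosinophils, is part of the central haematology panel.

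Section 9.2.6 notifies the investigator, and asks for a repeat within about 7 days, in three cases: ALC below 200, ANC below 1000, or total WBC above 20,000 cells/µL. If the repeat is also outside the limit, the investigator is told that the "results for the abnormal parameter have fallen below the acceptable threshold". The next step reads: "If ANC or total WBC counts are confirmed below the acceptable limits, the Medical Monitor will contact the treating investigator to request close monitoring". A confirmed ALC below 200 has its own rule: stop the drug, consult the Medical Monitor, and retest weekly until ALC is above 500.

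The liver rules follow in the same section. If "there are no apparent alternative causes for the finding, the investigational drug must be permanently discontinued" for any of four findings. The last is ALT or AST above 3x ULN "with the appearance of fatigue, nausea, vomiting, right upper quadrant pain or tenderness, fever, rash, and/or eosinophilia", with eosinophilia defined as above 5%.

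**The concern.** A mandatory stop rule needs someone who can see its input and is told to act on it. Eosinophils sit inside the blinded differential and trigger no alert, so the investigator, who must stop the drug, cannot know when this limb is met.

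The WBC text has a direction error. Its only limit is high, while every follow-up sentence describes a low result. The protocol evidently meant to watch for low counts: Section 5.1.2 justifies the visit schedule partly by the need to detect excessively low leukocyte counts, and the Medical Monitor step names total WBC. Sections 3.3.1 and 3.3.2 describe immunosuppression as the mechanism of both drugs. At stake are one element of a permanent liver stop and one element of the serious-infection follow-up.

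**Working it through.** This is a check of logic: each trigger is set against who can see it and which way its limit points.

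**1. The liver stop.** The routes to stopping in Sections 9.2.6 and 8.1 are:

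- ALT or AST above 8x ULN: visible.
- ALT or AST above 5x ULN: visible. Section 9.2.6 asks for confirmation within 2 weeks; Section 8.1 lists it without that condition.
- ALT or AST above 3x ULN with bilirubin above 2x ULN (both sections) or INR above 1.5 (Section 9.2.6): visible.
- ALT or AST above 3x ULN with a listed symptom: visible.
- ALT or AST above 3x ULN with eosinophilia above 5%: hidden.

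Eosinophilia decides alone only when ALT or AST is above 3x and up to 5x ULN, bilirubin is at most 2x ULN, INR is at most 1.5, no listed symptom is present and no alternative cause is apparent.

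Could someone else apply it? Section 9.4.9 names WBC and lymphocytes for central monitoring, not eosinophils. Section 5.1.4 gives the DMC an advisory review of laboratory data. Section 9.4 refers only generally to study-team monitoring. Section 9.2.6 lets the investigator order further liver tests, but names no differential and gives no exception to the blind. None of these assigns the check.

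**2. The low-WBC step.** To be flagged and repeated, total WBC must exceed 20,000. To start the Medical Monitor step, it must be confirmed below a limit. No value satisfies both, and no low on-treatment WBC limit exists. The 3000 floor in Section 6.2 is an entry exclusion at Screening or Baseline. Read literally, a confirmed WBC of 21,000 would be reported to the site as a fall.

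The ANC part of the same step works, as does the ALC rule. The uncovered case is therefore low WBC with ANC at least 1000 and ALC at least 200. At those two boundary values, neutrophils and lymphocytes total 1000 + 200 = 1200 cells/µL and no alert fires.

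**3. Why the fix needs a baseline and a lymphocyte exception.** Section 5.5.1 gives Phase 1 median ALC nadirs of 53.7% (0.25 mg) and 75.9% (0.75 mg) below baseline. Take a participant at the entry limits (WBC 3000, ALC 1000) and change nothing else:

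- 0.25 mg: ALC falls by 537 to 463; WBC = 3000 − 537 = 2463.
- 0.75 mg: ALC falls by 759 to 241; WBC = 3000 − 759 = 2241.

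Neither ALC reaches 200, so these falls are unalerted now. They are also pure drug effect: the non-lymphocyte count stays at 2463 − 463 = 2241 − 241 = 2000.

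The same fall raises the eosinophil percentage with no new eosinophils. If lymphocytes are a share s of WBC and fall by a fraction f, a pre-treatment percentage e becomes e / (1 − f × s). It reaches 5% when e = 5 × (1 − f × s). With s assumed to be 20 to 40% and other cells unchanged:

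- f = 0.537, s = 0.20: e = 4.46%.
- f = 0.759, s = 0.40: e = 3.48%.

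A pre-treatment share of about 3.5 to 4.5% could thus cross the line from lymphocyte loss alone. Section 3.1.1 also associates the disease with eosinophilia in 80% of patients. A single on-treatment percentage would mislead.

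**The case against.** The strongest reply is that both gaps are small and partly deliberate. ALC reduction is a known effect of BMS-986166, and the counts are withheld to protect investigators who also score the primary endpoint. Neutrophils and lymphocytes, the major WBC components, each have a low alert. A low-WBC alert could fire mainly in the BMS-986166 arms and hint at assignment. On the liver side, the affected participant is retested within 4 days and, once the elevation is confirmed, twice weekly. A confirmed elevation above 3x ULN is reported as an adverse event of interest, and Section 8.1 lets the investigator stop for any laboratory abnormality on judgment. Isolated eosinophilia would seldom be decisive in this population.

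Most of this stands and limits the point. The blind is sound, and the unblinding risk must shape the fix. It does not remove the fault: one mandatory limb has no one to apply it, and one step has no value that starts it.

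Three stronger inferences are not supported:

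- That the liver stop as a whole is disabled: every other trigger stays visible.
- That any participant with low WBC and ANC of 1000 or more goes unnoticed: an ALC below 200 is alerted and, if confirmed, stops the drug.
- That the alert limits conflict with the Section 8.1 rule on "Grade 2 or higher cardiac or bone marrow adverse events (with exception of ALC) according to the CTCAE version 5.0": this depends on grade cut-offs that the documents do not give.

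**Conclusion.** The point holds in narrow form and should be corrected. The eosinophilia limb cannot be applied as written. The total-WBC part of the Medical Monitor step can never start, and a confirmed high WBC would be described to the site as low.

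Both conclusions follow from the text and need no clinical assumption. Their size cannot be estimated from the documents, which give no rate for participants whose outcome would turn on the hidden value. Early data do not suggest many. In the 28-day BMS-986166 study (Section 3.2.1.5), ALT increases were judged drug-related in 3 participants and all drug-related events were mild. In the branebrutinib contraceptive study of 24 healthy women (Section 3.2.2.5), all ALT and AST changes were below 3x ULN. The number affected here could be zero. The lymphocyte calculations are illustrations: they use healthy-participant medians, an assumed lymphocyte share and unchanged other cells.

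**What to change.** 1. **Eosinophils.** When ALT or AST exceeds 3x ULN, have the existing central monitoring compare on-treatment eosinophils, as percentage and absolute count, with the participant's pre-treatment value. If new eosinophilia above 5% has appeared, tell the investigator, without values, that this limb is met. The investigator then judges alternative causes, including the dermatitis itself, and stops the drug if there are none.
2. **High WBC.** Give the 20,000 limit its own message, so that a high result is not reported as a fall.
3. **Low WBC.** Either add a low total-WBC limit, checked centrally and relayed only when lymphocytes do not explain the fall (for example, when WBC minus ALC has also dropped), or delete total WBC from the low-count step and rely on the ANC and ALC alerts. The documents give no on-treatment low value, so the sponsor would have to set one.

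The cost is a short amendment and a few central alerts. Haematology and chemistry are already drawn at every on-treatment visit and analysed centrally, so no new sample or visit is needed. The downside is a small unblinding risk if lymphocyte-driven WBC falls were relayed to sites, which the lymphocyte exception limits. Deleting total WBC avoids that risk but gives up a check on low WBC when ANC and ALC are above their alert limits.
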